### Study procedures:

**Brachial artery FMD:** Arterial measurements will be performed by imaging the brachial artery longitudinally using high-resolution duplex ultrasonography. Arterial vasodilatory responses to hyperemia (*i.e.*, FMD) will be examined by inflating a forearm cuff up to 250 mmHg for five minutes. Before, during and after rapid release of the cuff, brachial artery blood flow velocity and diameter will be continuously measured. In addition, during the FMD measurements, near-infrared spectroscopy (NIRS) probes will be placed on the forearm; the probe will be secured via an elastic tensor bandage which will be loosely wrapped around the site. These probes will stay attached to the participant for the duration of testing. The FMD procedure will be performed in duplicate.

**Glycocheck:** The Glycocheck video microscope instrument will be placed under the subject's tongue to measure capillaries, blood vessel density, red blood cell concentration, flow rate, and red blood cell penetration of the glycocalyx lining. Glycocheck is an FDA Class 1 Medical Device. This procedure takes approximately 1 hour to complete.

### **Study medications**

**Zanamivir:** Used as the study medication. Subjects will inhale 10mg of zanamivir twice daily for five days.

### **Sources of research material**

Sources will include the subject's medical history, physical exam, blood tests, brachial artery FMD, and Glycocheck. Demographic data (plus other related data: emergency contact person, pregnancy status), blood pressure, and anthropometrics (height and weight) will be measured. Each subject will donate up to 40 mL of blood.

### **Changes to existing therapies**

For scientific purposes, it would be best to have patients who are not on medications; however, it would neither be safe nor ethical to completely discontinue medications. Therefore, we will study patients on their existing drug therapy but will limit recruitment to patients on the fewest medications. Common medications in T2D (*e.g.*, insulin, metformin, gliptins, GLP-1 analogs, SGLT2i, antihypertensives, antidepressants, statins) will be considered during recruitment, analyses (*e.g.*, using covariate analysis) and interpretation.

### **Subject safety**

Should subjects exhibit changes in their health status across any system related or unrelated to the study treatment, [name], the safety officer, will be consulted for advice.

## **VIII. Potential Risks/Adverse Events**

### **The following are potential risks:**

**Venous blood draw:** The potential risks of a venous blood draw include infection, swelling and discomfort at the puncture site. Some bleeding may occur as well after the needle is removed. There is also the possibility of fainting, dizziness, and possible pain and bruising as a result of the puncture. These risks will be greatly minimized by using sterile procedures and having an experienced registered nurse do the blood draw. Risk of bleeding is reduced by applying pressure at the site of puncture. Bruising is treated with ice. Fainting is prevented by drawing blood in the semi-recumbent position.

**Brachial artery FMD with NIRS:** This is a measurement of endothelial function. There are no risks associated with this procedure. When assessing FMD, the blood pressure cuff will squeeze the arm tightly; however, any discomfort will be alleviated as soon as the pressure in the cuff is released.

**Glycocheck:** This procedure poses no risks.

**Zanamivir:** Potential side effects are outlined in package insert. Medication should not be administered to individuals with COPD or asthma.

### **Protection against risks**

Risks to loss of confidentiality are reduced by assigning all subjects a data identifier code. Hard copies of data are stored in a locked office, and only the study personnel have access to the locked files. Individual names or initials are not used in any discussions or publications of the data. We have assembled a research team which includes scientists, physicians, and clinician-scientists with significant experience in human research and cardiometabolic diseases to help anticipate and reduce the risks to subjects.

### **Plan for reporting study deviations**

Any minor problem/deviation will be summarized and reported to the IRB within five working days of awareness, including any event that does not: 1) increase the risk to the subject, 2) decrease the benefit to the subject, or 3) significantly affect integrity of the research data. Any major problem/deviation will be summarized and reported to the IRB within five working days of awareness, including any event that: 1) increases the risk to the subject, or 2) significantly affects integrity of the research data.

### **Stopping rules**

We will stop an individual study if a serious adverse event occurs. If four or more subjects experience a serious adverse event requiring termination of the study, the study will be stopped and the events will be discussed with the IRB to determine whether it is appropriate to continue and/or determine appropriate modifications to the protocol to avoid further adverse events. All unanticipated serious adverse events will be submitted for review according to current protocols. The medication will be discontinued at the discretion of the study safety officer.

### **Definition of serious adverse event (SAE)**

A SAE is classified as any untoward medical occurrence that, at any dose, meets any of the following criteria (a – f):

a. Results in death

b. Is life-threatening

The term 'life-threatening' in the definition refers to an event in which the subject was at risk of death at the time of the event, it does not refer to an event which hypothetically might have caused death if it were more severe.

c. Requires inpatient hospitalization or prolongation of existing hospitalization

A hospitalization or prolongation of hospitalization will not be regarded as a serious adverse event if

at least one of the following exceptions is met:

- The admission results in a hospital stay of less than 12 hours
- The admission is pre-planned
- The admission is not associated with an adverse event related to the study medication or study procedures as determined by the study safety officer and data safety monitoring board.

d. Results in persistent or significant disability / incapacity

Disability means a substantial disruption of a person's ability to conduct normal life's functions.

e. Is a congenital anomaly / birth defect

f. Is another serious or important medical event as judged by the investigator.

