**Frequency of monitoring, including any plans for interim analysis and stopping rules**

Monitoring will include enrollment, attrition, efficacy endpoints, and adverse events. The safety officer will routinely review the safety information related to this project at three-month intervals. In addition to monitoring by the PIs, study physician, study coordinator, and safety officer, the DSMC conducts its reviews on a semiannual basis. The frequency of the structured data review for this study can be summarized in the following table:

Data type	Frequency of review
Subject accrual (adherence to protocol regarding demographics, inclusion/exclusion)	At the end of each recruitment
Adverse event rates (injuries)	semi-annually
Compliance to supplementation	semi-annually
Stopping rules report regarding statistical power implications of dropouts and missing data	semi-annually
IRB review	annually
DSMC review	semi-annually

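### Under the hospitalization criterion, a judgement that an admission is unrelated removes its serious status, so the NIH report and the SAE listing can omit a real hospitalization

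*Combined protocol and SAP*

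**What the plan says.** The definition in Section VIII, Definition of serious adverse event (SAE), opens broadly: "A SAE is classified as any untoward medical occurrence that, at any dose, meets any of the following criteria", followed by criteria a to f. Nothing in that opening refers to cause.

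Criterion c covers inpatient hospitalization and its prolongation. It is qualified by three exceptions, and meeting any one of them is enough for the admission not to count. The first is a stay under 12 hours and the second is an admission arranged in advance. The third is "The admission is not associated with an adverse event related to the study medication or study procedures as determined by the study safety officer". The full wording requires two parties, since the finding is to be made "as determined by the study safety officer and data safety monitoring board".

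Criteria a, b, d and e (death, threat to life, disability, congenital anomaly) have no relatedness condition. Neither does criterion f: "Is another serious or important medical event as judged by the investigator".

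SAE status is used elsewhere. Section VIII, Stopping rules, says "We will stop an individual study if a serious adverse event occurs", read here as stopping that subject, and adds a study-level rule: "If four or more subjects experience a serious adverse event requiring termination of the study, the study will be stopped". Section XII, Plan for adverse event reporting, sends SAEs to the NIH, unanticipated events to the IRB, and serious and non-serious events alike to the DSMC.

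**The concern.** Seriousness should record what happened to the subject. Relatedness is a separate judgement about why. The first two exceptions under criterion c are matters of fact, namely length of stay and whether the admission was planned. The third is an opinion about cause, and it can override the outcome. That departs from the definition's own opening sentence, and it happens at hospitalization only.

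The opinion also has little to rest on. All 20 subjects receive zanamivir and are compared with their own baseline, so no concurrent control group shows how often such admissions occur without the drug. In a study this small, one admission could be the whole SAE listing, and reclassifying it would change the reported result from one SAE to none. The NIH report would fall away with it, because that report is triggered by seriousness alone.

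**Working it through.** **Step 1. Logic of criterion c.** The protocol states no figure to reproduce, so the check begins with the text. Take an unplanned admission of 12 hours or more that meets none of a, b, d, e or f.

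| Exception | Judged related | Judged unrelated by both parties |
|---|---|---|
| Stay under 12 hours | not met | not met |
| Planned in advance | not met | not met |
| Not associated with a related event | not met | met |
| SAE under criterion c? | yes | no |

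The two columns differ only in the causality judgement, so that judgement alone decides the classification. No other section of the protocol overrides the third exception.

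**Step 2. What still happens to the reclassified event.**

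- DSMC: receives it, because non-serious events are also reported there (Section XII, Plan for adverse event reporting).
- IRB: receives it if unanticipated (same section).
- Safety officer: is consulted on changes in health, whether related or not (Section VII, Subject safety), and can act: "The medication will be discontinued at the discretion of the study safety officer".
- Investigator: may still class it as serious under criterion f.
- NIH report and SAE listing: no longer required to include it.
- Individual stop: no longer required on the strength of criterion c. If the admission counts as an SAE until it is cleared, the stop may already have applied.

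**Step 3. How often this could arise.** The sample size of 20 comes from Section VI. The protocol gives no admission rate, so the five-day risk per subject, p, of such an admission is an assumption, with a range of 0.1% to 0.5%. The share q judged unrelated by both parties is also assumed, from one half to all.

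Formulas: annualised rate = p × 365/5 = 73p; expected number = 20p; P(at least one) = 1 − (1 − p)^20; P(at least one reclassified) = 1 − (1 − pq)^20. The chances of two or more and of four or more are binomial tails with n = 20.

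| p | Per person-year | Expected in 20 | At least 1 | At least 2 | At least 4 |
|---|---|---|---|---|---|
| 0.001 | 0.073 | 0.02 | 0.0198 | 0.00019 | 5 × 10⁻⁹ |
| 0.002 | 0.146 | 0.04 | 0.0392 | 0.00074 | 8 × 10⁻⁸ |
| 0.005 | 0.365 | 0.10 | 0.0954 | 0.0045 | 3 × 10⁻⁶ |

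At least one reclassified event:

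- p = 0.001, q = 0.5: 1 − 0.9995^20 = 0.0100
- p = 0.001, q = 1: 1 − 0.999^20 = 0.0198
- p = 0.005, q = 0.5: 1 − 0.9975^20 = 0.0488
- p = 0.005, q = 1: 1 − 0.995^20 = 0.0954

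The range is therefore 1.0% to 9.5%. The chance of four or more such admissions is below 0.001%, so the four-subject rule is not realistically affected.

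**The case against.** The best defence is that an explicit exception to a general rule is a design choice. It needs two parties, and the safety officer is described as independent and outside the key personnel. The event remains visible to those who monitor the study. No endpoint, estimate or sample size is touched. The eligibility criteria exclude cardiovascular, renal, hepatic and autoimmune disease, active cancer, asthma and COPD, which points to the lower end of the assumed risk. All of this stands and limits the size of the point. It does not explain why cause should decide seriousness at one criterion and at no other.

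A reader might infer more than the documents support:

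- **That the investigator can declassify an admission alone.** The exception requires the safety officer and the board. The protocol describes a DSMC that sets up such boards but does not say that one exists for this trial. Read strictly, without a board determination the exception is not met and the admission stays an SAE. Reclassification therefore presumes that some body acts as the board.
- **That a determination must wait for routine review.** The protocol does say "The safety officer will routinely review the safety information related to this project at three-month intervals", and the treatment course is only five days. But the safety officer is also consulted when a subject's health changes, and reviews the investigators' reports with a view to ad hoc review (Section XII, Qualifications and responsibilities of the safety officer). No deadline is written, but the routine intervals do not establish a delay.
- **That hospitalizations disappear from oversight, or that the study stopping rule is disabled.** Steps 2 and 3 of the working show neither.

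**Conclusion.** The point holds as a defect in the wording of criterion c. An unplanned admission of 12 hours or more that meets no other criterion loses its serious status solely because it is judged unrelated. The consequence is confined mainly to the NIH report and the SAE listing, either of which could omit a real hospitalization.

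Confidence in the reading of the text is high. The 1.0% to 9.5% is only as good as the assumed admission risk and the assumed share judged unrelated, and the exclusion criteria favour the lower part of that range. The reading also assumes that a body acting as the board takes part in the determination. The correction is worth making because it is cheap and the present rule can produce a wrong listing. The risk itself is not large.

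**What to change.** Delete the third exception under criterion c, so that an unplanned admission of 12 hours or more is an SAE whatever its cause. Record relatedness in a separate field that never changes seriousness and never removes an event from the SAE listing.

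Leave the individual stop in Section VIII, Stopping rules, as written. It has no relatedness test at present. Making it discretionary for unrelated events, to spare subjects with incidental admissions, would also weaken the stop after an unrelated life-threatening or disabling event.

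The cost is a wording change, one data field and, at the assumed rates, most likely zero or one extra SAE report. There is also a small chance, the same 1.0% to 9.5%, that at least one subject is stopped after an unrelated admission that would now be excepted. Section VI plans 20 subjects against 18 needed, so if one such stop cost the final assessment it would use one of the two places (20 − 18 = 2) allowed for drop-out. No extra visits or staff are needed.

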### **Breach of confidentiality**

Subject confidentiality will be rigorously maintained. The data collected as part of this study will be for research only. It will be de-identified after collection. Confidentiality of data will be assured by coding of unique subject identities and that coding will be known only to the research team, including the use of secure files, locked in an office, and a unique subject coding system. The original study data will be kept in locked in an office (hard copy) or entered into a secure computer database password protected under a secure server space allocated for use by only the study team (electronic). Furthermore, data analysis will be appropriately blinded and any individual data presented in manuscripts will also be presented in an anonymous nature. No identifying information will be disclosed. Confirming with University of Missouri policy, all research records will be retained for a period of seven years following completion of the study.

All protocols and techniques to be used will be approved by the Institutional Review Board (IRB) prior to initiation of any studies. Each subject will give written informed consent after all questions have been answered by a study team member. The consent form will also include a statement guaranteeing confidentiality. Adverse event reports and annual

summaries will not include subject-identifiable material. No information will be given to anyone without permission from the subject. Electronic communication with study team members will involve only coded, unidentifiable information. Any unanticipated breach of confidentiality will be summarized and reported to the IRB within five working days of awareness.

## **IX. Anticipated Benefits**

There may be no benefit to the subjects in this study. These data will aid in the understanding of the efficacy of neuraminidase inhibition as therapeutic strategy for restoring endothelial function in T2D patients as well as determining the efficacy of treating glycocalyx degradation as a means of improving endothelial function in T2D.

## **X. Compensation**

We have completed multiple clinical studies involving human subjects with adherence rates of greater than 95% and subject retention rates of greater than 85%. We utilize a validated retention strategy published by Jeffrey et al (Am J Clin Nutr. 2003;78(4):684-689) that has been successful. With respect to subject honoraria, subjects will be paid \$50 after completion of the screening visit, \$250 after the baseline visit, and \$300 after the final visit. Thus, a total compensation of \$600 will be provided as study events are completed.

Visit	Compensation
Screening	\$50
Pre-assessment	\$ 250
Post-assessment	\$ 300

## **XI. Costs**

The subjects will not be charged for any procedures that are part of this research study. The costs of the study will be covered by a federal grant from the NIH.

## **XII. Data Safety Monitoring Plan**

The data safety monitoring plan (DSMP) for this study is focused on the supervision performed by the PIs, the Co-Investigator, [name], and the safety officer, [name]. Monitoring will include enrollment, attrition, efficacy end-points, and adverse events.

### **Plan for data management**

A password-protected database will be used to manage all study data. To ensure confidentiality only subject ID numbers will be entered into the database. Signed informed

consent forms are kept in a locked office. Participants will not be individually identified in any publication. Participants' right to privacy will be protected.

**Frequency of monitoring, including any plans for interim analysis and stopping rules**

Monitoring will include enrollment, attrition, efficacy endpoints, and adverse events. The safety officer will routinely review the safety information related to this project at three-month intervals. In addition to monitoring by the PIs, study physician, study coordinator, and safety officer, the DSMC conducts its reviews on a semiannual basis. The frequency of the structured data review for this study can be summarized in the following table:

Data type	Frequency of review
Subject accrual (adherence to protocol regarding demographics, inclusion/exclusion)	At the end of each recruitment
Adverse event rates (injuries)	semi-annually
Compliance to supplementation	semi-annually
Stopping rules report regarding statistical power implications of dropouts and missing data	semi-annually
IRB review	annually
DSMC review	semi-annually

**Plan for adverse event reporting:**

Serious adverse events will be reported to the NIH. Unanticipated events will be reported to the IRB, and both serious and non-serious adverse events will be reported to the MU School of Medicine DSMC. For reporting to the DSMC, adverse events will be categorized and classified according to the Common Terminology Criteria for Adverse Events Scale (CTCAE v3.0). Safety reports will be sent to the safety officer. The PIs will be responsible for assembling the data and producing these reports, as well as assuring that all parties obtain copies of these reports.

**Qualifications and responsibilities of the safety officer:**

[name], Associate Professor of Clinical Medicine, Division of Endocrinology, and board-certified endocrinologist will serve as the independent safety officer for this project. [name] is an experienced patient-oriented investigator, who is not part of the key personnel involved in this project but is familiar with all the proposed methodologies and their potential risks to human subjects. His expertise is in cardiovascular function and diabetes. As safety officer, [name] will review eligibility criteria with the PIs and [name]. He will review all reports sent by the PIs to determine whether there is any corrective action, trigger of an ad hoc review, or stopping rule violation that should be communicated to the University of Missouri IRB and the Data and Safety Monitoring Committee. In addition, the safety officer may comment on whether the study investigators need to report any specific out-of-range laboratory data.

**MU data and safety monitoring committee (DSMC)**

The MU School of Medicine DSMC was formed by the MU Institute for Clinical and Translational Science and activated as an advisory committee within the MU School of

Medicine. Its structure and processes are consistent with NIH guidelines. The DSMC helps investigators, and MU research compliance oversight mechanisms protect human-research participants and ensure the integrity and scientific validity of research data. The DSMC provides education for investigators, research teams, and faculty regarding data and safety monitoring; reviews proposed Data and Safety Monitoring Plans; establishes Data and Safety Monitoring Boards; conducts independent, interim reviews of study safety and progress; and makes recommendations concerning the continuation of studies, including recommendations regarding the modification, suspension, or termination of a study.

